#### **4.1.4. Definition of Study Time Points**

Visits will consist of the screening/dispensing visit, several follow-up visits, and the Exit visit. There is also the possibility for unscheduled visits. The following definitions will be used for classifying visits:

- Baseline (Day 1) will be defined as the screening/dispensing visit.
- Scheduled follow-up visits will include any of the following visits:
  - 2-Week Follow-up Visit
  - 1-Month Follow-up Visit

- 2-Month Follow-up Visit
- 3-Month Follow-up Visit

Any unscheduled visit (which may include the exit visit) which occurs after baseline will be considered a follow-up visit (but not a scheduled follow-up visit) for all analyses. For example, if a slit-lamp finding greater than Grade 2 occurs during an unscheduled visit after baseline, it will be included in the analyses for the primary safety endpoint.

## **4.2. Subject Disposition(s)**

Study disposition of all subjects who sign the informed consent will be summarized. The summary will include:

- The overall number of subjects who sign informed consent (i.e., subjects screened).
- The following will be summarized for each intervention separately as well as overall.:
  - Subjects randomized.
  - Subjects dispensed.
  - Subjects who completed the 3-Month Follow-up Visit.
  - Subjects who discontinued the study.
  - Subjects assigned to each Study Population (ITT, PP, Safety).

A separate summary of eye accountability, including eyes enrolled but not dispensed, eyes completing each visit (active lens wearers), and discontinuation (with reasons), will be provided for the ITT Population, by treatment and overall.

Subject study disposition information will also be listed.

### **4.2.1. Protocol Deviations**

In the event a protocol deviation occurs, the date of and reason for deviations must be documented in all cases. Significant or major protocol deviations impacting the rights or safety of the subject or the integrity of the study must be reported by the Investigator to the IRB/EC and Medical Monitor immediately. Reporting of all other protocol deviations must adhere to the requirements of the governing IRB/EC. Unless the protocol deviations put the subject at risk or the subject's condition requires that they be discontinued from the study, subjects may continue to participate until the end of the study.

Major protocol deviations will be summarized by subject. All protocol deviations will be provided in a corresponding listing.

## **4.3. Baseline Characteristics and Subject History**

Demographics and baseline characteristics will be summarized descriptively by intervention and overall, for the ITT, PP, and Safety Populations. If the study populations are equivalent, then the PP and Safety Population summaries will not be produced. All relevant data will also be produced in a listing.

#### **4.3.1. Demographics**

Demographic variables collected during Day 1, including age (years), sex, childbearing potential, race, and ethnicity, will be summarized. Age will be based on the age of the subject on the date the informed consent is signed, and also summarized categorically by decade ( $\leq 20$ ,  $>20 \leq 30$ ,  $>30 \leq 40$ , etc.).

#### **4.3.2. Baseline Lens and Lens Care History**

##### **4.3.2.1. Subject Level Summary**

A summary will be provided which includes the following baseline information from Day 1:

- Average Daily Wear Time (hours/day).
- Average Hours of Comfortable Wear (hours/day).
- Lens Care System Routinely Used.

##### **4.3.2.2. Eye Level Summary**

A summary will be provided which includes the following baseline information from Day 1:

- Current Lens Brand.
- Habitual Lens Power.
  - Sphere (D).
  - Base Curve (mm).
- Subject Wearing Lens at Screening (yes/no) and Time Worn (hours).

A separate summary of baseline refraction (without lenses, in minus cylinder notation) will be provided, and will include: sphere, cylinder, axis, and spherical equivalent.

#### **4.4. Study Intervention and Concomitant Medications**

##### **4.4.1. Extent of Exposure**

As is customary for contact lens solution trials, treatment exposure will not be summarized.

##### **4.4.2. Treatment Compliance**

As is customary for contact lens solution trials, treatment compliance will not be summarized.

##### **4.4.3. Concomitant Medications**

All medications for conditions taken within 30 days of signing the informed consent and any ongoing medication(s) taken during the study/medical treatment given for the treatment of an adverse event (AE) during the study should be recorded.

For reporting purposes, concomitant medications will be defined as medications taken on or after the Day 1. This includes all medications initially taken prior to Day 1 but with a stop date that is either missing or after Day 1. Those medications where the stop date is documented as prior to Day 1 will be classified as prior medications. The prior medications will be in the study database but will not be included in any summary reports nor listed.

When only a missing or partial date for a medication is available, the following rule will be applied for classifying the medication as concomitant or prior and for deriving duration, if necessary:

- For the start date:
  - If year, month, and day are missing then use the minimum of the subject's first visit date or the consent date.
  - If year is present and month is missing, then use January 1.
  - If only day is missing, impute the first day of the month.
- For the end date:
  - If year, month, and day are missing then use the subject's last visit date.
  - If year is present and month is missing, then use December 31.
  - If only day is missing, then use the last day of the month.
  - Do not expand the record past the subject's last visit.
- The original missing or partial date, the imputed complete date, and the indicator variable that indicates which dates were imputed will be retained in the database.

Concomitant medications will be reported by Anatomical Therapeutic Chemical classification system Level 2 (main therapeutic group) and preferred drug name (often the generic drug name) from the WHODD. The report of all concomitant medications taken during the study will be provided as listings only.

#### **4.4.4. Study Lens Dispensation**

The number and proportion of subjects with lenses dispensed at each visit will be summarized, along with type of lens dispensed at each visit. A separate summary will be provided that summarizes the lens power (i.e sphere and base curve) of the dispensed lenses by visit at the eye level.

#### **4.4.5. Lens Replacement**

The number and proportion of eyes with any lenses replaced will be summarized for each treatment group individually by subjects who (1) completed the study, (2) discontinued the study, and (3) either completed or discontinued the study (i.e., overall). This summary will include a categorical summary counting the number of replacement lenses needed for each eye. Additionally, the primary reason and type of lens dispensed as replacement will be reported by count and percentage (using the total number of lenses replaced as the denominator). Finally, this summary will include the lens power across all replaced lenses.

### **4.5. Primary Estimand Analyses**

The primary objective of the study will depend on successfully demonstrating non-inferiority of Test vs. Control in four different primary estimands, one of which is safety-related and the other three of which are efficacy-related.

#### 4.5.1. Definition of Endpoints

The safety-related endpoint is as follows:

- The proportion of eyes with any slit-lamp findings greater than Grade 2 over all follow-up visits (scheduled and unscheduled).
  - At each follow-up visit, graded slit-lamp findings will be assessed for each eye using Grades 0 through 4. Using only the non-missing observations from all follow-up visits, each eye will be classified with respect to findings greater than Grade 2 at any visit (Absent, Present).

The efficacy-related endpoints are as follows:

- Overall comfort averaged over all scheduled follow-up visits.
  - At each follow-up visit, overall comfort will be assessed for each eye on a scale from 0 to 100, with 100 denoting the most favorable response. For each eye, mean overall comfort over all follow-up visits will be computed as the average of the non-missing values over all scheduled follow-up visits
- Vision averaged over all scheduled follow-up visits.
  - At each follow-up visit, vision will be assessed for each eye on a scale from 0 to 100, with 100 denoting the most favorable response. For each eye, mean vision over all follow-up visits will be computed as the average of the non-missing values over all scheduled follow-up visits.
- The proportion of eyes with a maximum degree of front surface deposits grade of  $\leq 2$  over all scheduled follow-up visits.
  - At each follow-up visit, the degree of front surface deposits will be graded for each eye as 0, 1, 2, 3, or 4. Using only the non-missing observations from scheduled follow-up visits without imputation, each eye will be classified with respect to the maximum grade of front surface deposits ( $\leq 2$ ,  $> 2$ ) observed over all follow-up visits.

#### 4.5.2. Main Analytical Approach

All contrasts and differences will be calculated as Test – Control. All observations will be treated as independent (e.g. each eye and/or each subject).

##### 4.5.2.1. Graded Slit-Lamp Findings > Grade 2

Greater than Grade 2 findings (Absent, Present) overall all follow-up visits will be summarized at the eye level by treatment using categorical summary statistics for the Safety Population. A one-sided upper 97.5% confidence limit around the difference in “Present” proportions between the Test and Control treatment groups will be constructed using the Newcombe-Wilson score method.

If the upper confidence limit is less than 5.0% or if no findings greater than Grade 2 are observed in either treatment group, then the null hypothesis that the Test solution is not noninferior will be rejected, and the Test solution will be statistically successful in this outcome.

#### 4.5.2.2. Overall Comfort

Mean overall comfort over all follow-up visits will be summarized at the eye level by treatment using continuous summary statistics for the ITT Population. A one-sided lower 97.5% confidence limit around the difference in means between the Test and Control treatment groups, computed using an analysis of variance model including the fixed factors of treatment, site, and lens group will be displayed.

If the lower confidence limit is greater than -5.0, then the null hypothesis that the test solution is not noninferior will be rejected, and the test solution will be statistically successful in this outcome.

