6.1.1 Screening/Dispensing Visit

After obtaining written informed consent, prospective subjects will be screened to determine whether they meet the entry criteria for the study.

The Screening/Dispensing Visit will proceed as follows:

- a. Collect demographic information as required by the RTSM system
- b. Collect the following baseline lens/lens care history information and lens wear parameters from the subject:
 - Average daily wearing time
 - Hours lenses worn on the day of this visit

- Average hours per day of comfortable wear
- Current lens brand, sphere power and base curve
- Current lens care products
- c. For females of child-bearing potential, inform the potential subject they must use an effective method for birth control during the study and for 2 weeks following the last visit, in a manner that risk of contraceptive failure is minimized. Abstinence is allowed as a birth control method.
- d. Perform the following baseline assessments (without lenses; remove the lenses if the subject wore lenses to the visit):

NOTE: All VA measurements MUST be made using a phoropter.

- Spherocylindrical refraction
- High contrast spectacle-corrected visual acuity (BSCVA)
- Keratometry
- e. Perform a slit-lamp examination (remove the lenses if the subject wore lenses to the visit). Record and sketch any scars and slit-lamp findings greater than Grade 2 in the subject's source document.
- f. If the subject continues to be eligible, have the subject complete and initial the following form:
 - The Initial Lens Performance Assessment Form (Worn Lens Performance Rating Scales), including use of rewetting drops.
- g. Complete the Initial Symptoms/Complaints Form (Worn Lenses Symptoms/Complaints Form).
- h. Dispense three pairs (two for back up only) of the subject's habitual contact lenses. Explain to the subject that the used lenses will be removed at the follow-up visits and returned to the Sponsor.
- i. Instruct subject to insert study lenses

NOTE: wait 2-3 minutes for the new contact lenses to settle on the eye before proceeding

- j. Instruct subject to complete Lens Performance Assessment Form (Abbreviated version: Study Lenses Lens Performance Rating Scale).
- k. Complete the Symptoms/Complaints Form (Study Lenses Symptoms/Complaints).
- 1. Record the following:

- Dispensed lens type (brand), sphere power, base curve
- High contrast distance lens VA
- Over-refraction and distance VA
- Lens wettability
- Lens centration
- Lens movement

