8.6 Statistical Analysis

8.6.1 Methods of Analysis

8.6.1.1 General Methods

Continuous data will be summarized using sample size (n), mean, standard deviation (SD), median, minimum, and maximum. Categorical data will be presented using the total counts for each category and corresponding percentages. The denominator for each percentage will be the number of subjects or eyes with non-missing data unless otherwise indicated.

As is customary for contact lens solution trials, eyes will be treated as independent sampling units in eye level analyses unless otherwise noted.

Listings of data will be produced in addition to tables of summary statistics.

8.6.1.2 **Overall Comfort**

At each follow-up visit, overall comfort will be assessed for each eye on a scale from 0 to 100, with 100 denoting the most favorable response. For each eye, mean overall comfort over all follow-up visits will be computed as the average of the non-missing values over all scheduled follow-up visits. Missing data will not be imputed for the primary analysis. Mean overall comfort over all follow-up visits will be summarized at the eye level by treatment using continuous summary statistics for the ITT Set in a table. A one-sided lower 97.5% confidence limit around the difference in means between the Test and Control treatment groups, computed using an analysis of variance model including the fixed factors of treatment, site, and lens group will be displayed. If the lower confidence limit is greater than -5.0, then the null hypothesis that the test solution is not noninferior will be rejected, and the test solution will be statistically successful in this outcome.

As a sensitivity analysis, the PP Population will be analyzed for this endpoint.

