2.0 Slit-Lamp Examination

The following parameters will be assessed during the Slit-Lamp Examination (without lenses):

Epithelial Edema

- 0 None: No epithelial or sub-epithelial haziness. Normal transparency.
- 1 Trace: Barely discernible localized epithelial or sub-epithelial haziness.
- 2 Mild: Faint but definite localized or generalized epithelial haziness.
- 3 Moderate: Significant localized or general epithelial haziness.
- 4 Severe: Definite widespread, epithelial cloudiness giving dull glass appearance to cornea, or numerous coalescent bullae.

Epithelial Microcysts

- 0 None: no microcysts; normal transparency.
- 1 Trace: 1 to 20 microcysts; barely discernible local epithelial haziness.
- 2 Mild: 21 to 50 microcysts; faint but definite localized generalized haziness.
- 3 Moderate: 51 to 100 microcysts; significant localized or generalized haziness.
- 4 Severe: > 100 microcysts; definite widespread epithelial cloudiness giving a dull glass appearance to the cornea or numerous coalescing bullae.

Stromal Edema

- 0 None: no oedema.
- 1 Trace: just detectable clouding.
- 2 Mild: faint corneal striae (2 or fewer).
- 3 Moderate: pronounced corneal striae (3).
- 4 Severe: folds in Descemet's membrane pronounced striae.

Endothelial regularity

- 0 None: regular endothelial mosaic.
- 1 Minimal: isolated difference in cell size.
- 2 Mild: just noticeable variation in cell size or bumpiness of cell layer.
- 3 Moderate: easily detected difference in cell size or bumpiness of cell layer.
- 4 Severe: noticeable cell layer bumpiness and loss of definition of cell borders.

Corneal Staining

Corneal staining must be assessed after the instillation of fluorescein. A Wratten Gel Filter will be provided by the Sponsor for the evaluation of corneal staining. The Wratten Gel Filter must be used as a barrier filter in the observation pathway, in combination with the cobalt blue filter.

- 0 None: No fluorescein staining.
- 1 Trace: Minimal superficial staining or stippling, and non-coalescing. Includes superficial foreign body staining.
- 2 Mild: Lightly coalescent or diffuse punctate staining, with no stain diffusion into stroma.
- 3 Moderate: Significant or densely coalescent punctate staining, including slight diffusion of stain into stroma.
- 4 Severe: Severe abrasion or erosion with loss of epithelial substance. Marked and rapid diffusion of stain into stroma.

Limbal Injection

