#### 4.5.2.3. Vision

Vision will be analyzed using the methods described above for overall comfort.

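### Optional precision gain: the comfort and vision ANOVAs could adjust for the pre-randomisation habitual-lens rating, if the screening form carries those two scales

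*SAP*

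**What the plan says.** SAP 4.5.2.2 bases the comfort decision on a one-sided lower 97.5% limit "computed using an analysis of variance model including the fixed factors of treatment, site, and lens group". SAP 4.5.2.3 adds: "Vision will be analyzed using the methods described above for overall comfort". Protocol 8.6.1.2 and 8.6.1.3 agree ("computed using an analysis of variance model including the fixed factors of treatment, site, and lens group will be displayed"). SAP 4.5.3 repeats the model in the sensitivity analyses, and SAP 4.9.1 repeats the primary analyses by lens group. SAP 4.10 lists no change on this point.

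At Screening/Dispensing, Protocol 6.1.1 step f has a subject who is still eligible complete "The Initial Lens Performance Assessment Form (Worn Lens Performance Rating Scales), including use of rewetting drops". Randomisation through the RTSM system comes later in the same visit, under step l. Appendix A schedules the habitual-lens form at this visit only.

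Protocol Appendix B 7.0 gives two lists of scales. The full list includes Overall Comfort (scale 3) and Vision (scale 12). The abbreviated list has only scales 1, 2 and 5. Protocol 6.1 and Appendix A tie the abbreviated form to the study lenses and list the habitual-lens form separately.

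Rating by eye is stated for follow-up (SAP 4.5.1: "At each follow-up visit, overall comfort will be assessed for each eye on a scale from 0 to 100"). Nothing says whether the screening form is also by eye.

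**The concern.** A baseline value of the same scale, measured before randomisation, is usually a useful covariate for a rating averaged over follow-up. It cannot be affected by treatment, and it removes outcome variation that site and lens group do not explain. Here such a value appears to be collected and then left out of both models.

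The stake is the distance from the estimated difference to its lower limit. A shorter distance leaves more room above the -5 margin. That matters mainly if Test is truly somewhat worse than Control, because the planned 99% power assumes a true difference of exactly 0 and all four co-primary endpoints must succeed.

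**Working it through.** **Inputs from the documents.** 300 eyes (150 subjects) per arm, one-sided alpha 0.025, SD 13.264 for comfort and 11.7 for vision, true difference 0 (SAP 2.2.1, 2.2.2); margin -5 (SAP 2.1.1, 2.1.2); eyes taken as independent (SAP 2.2, 4.1, 4.5.2).

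**Assumed inputs.** The correlation r between baseline rating and follow-up mean, after site and lens group, is not given, so a range is shown. The SDs come from the sponsor's Study #872 and are assumed not to be baseline-adjusted already; the documents do not say. A true difference of -2 is used only for illustration.

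**Plan's own figure.** Standard error = SD × √(2/300). For comfort, 13.264 × 0.08165 = 1.083. The noncentral t with 598 df and noncentrality 5/1.083 gives power 99.6%. The same steps for vision give a standard error of 0.955 and power just under 99.95%. Both reproduce the stated 99%.

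**Effect of the covariate.** Residual SD = SD × √(1 − r²). Distance to limit = t(0.975, df) × residual SD × √(2/n). Lowest passing estimate = −5 + distance. For comfort at r = 0.5: 13.264 × 0.8660 = 11.487; 1.9639 × 11.487 × 0.08165 = 1.84; −5 + 1.84 = −3.16.

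Comfort, 300 independent eyes per arm:

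| r | Distance to limit | Lowest passing estimate | Power at 0 | Power at -2 |
|---|---|---|---|---|
| 0 (planned) | 2.13 | -2.87 | 99.60% | 79.0% |
| 0.1 | 2.12 | -2.88 | 99.62% | 79.4% |
| 0.2 | 2.08 | -2.92 | 99.70% | 80.6% |
| 0.3 | 2.03 | -2.97 | 99.80% | 82.6% |
| 0.5 | 1.84 | -3.16 | 99.96% | 89.1% |

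For vision, r = 0, 0.3 and 0.5 give distances of 1.88, 1.79 and 1.62, and power at -2 of 88.0%, 90.8% and 95.2%.

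The fitted models would have 573 df (600 − 1 − 1 − 21 − 4, for 22 sites and five lens groups), or 572 with the covariate. Power then moves by 0.01 percentage point or less.

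**If the two eyes are not independent.** In the extreme case of fully correlated eyes the effective n is 150 per arm (298 df). The figures below apply only if the standard error reflects this, which the planned one does not.

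| r | Comfort distance | Power at 0 | Power at -2 |
|---|---|---|---|
| 0 | 3.01 | 90.2% | 49.7% |
| 0.3 | 2.88 | 92.7% | 53.5% |
| 0.5 | 2.61 | 96.4% | 61.6% |

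**Bias and type I error.** In 20,000 simulated comfort trials at a true difference of -5, with independent eyes and r = 0.5, the rejection rate was 2.48% without the covariate and 2.45% with it. Both mean estimates were about -5.00, and the SD of the estimate fell from 1.086 to 0.941. A separate simulation of 10,000 trials with 22 sites and five lens groups as fixed factors gave power at -2 of 79.2% against 82.2% (r = 0.3) and 78.8% against 88.9% (r = 0.5).

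**The case against.** The strongest objection is that this is a preference, not a defect. Both stratification factors are already in the model, and omitting a pre-randomisation covariate from a randomised comparison of means does no harm. At the planned difference of 0 almost nothing is gained with independent eyes. The larger gains need a true difference below 0 and a substantial r, and the documents supply neither. This stands, and it is why the point is optional.

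The second objection is that the form cannot be seen. SAP 4.3.2 lists no habitual-lens performance rating among its baseline summaries. SAP 4.9 expressly includes habitual-lens symptoms from screening but says nothing similar for lens performance. This does not contradict the inference from Appendix B 7.0, but the SAP does not confirm it. The fix therefore starts with the form.

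The third is that the rating may be noisy. It reflects a worn lens and the subject's own care product. Some subjects may arrive without lenses, as SAP 4.3.2.2 allows ("Subject Wearing Lens at Screening (yes/no) and Time Worn (hours"). The form also follows step e, "Perform a slit-lamp examination (remove the lenses if the subject wore lenses to the visit"), and Appendix B 2.0 states: "Corneal staining must be assessed after the instillation of fluorescein". At r of 0.1 to 0.2, comfort power at -2 rises by only 0.4 to 1.6 percentage points.

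A reader might infer that the omission biases the comparison or leaves the trial underpowered. Neither follows: the estimate is unbiased without the covariate, and the stated power is reproduced. A reader might also take the absence of harm here as clearing the ANOVA as a whole. It does not. The model treats a subject's two eyes as independent. At an assumed between-eye correlation of 0.5, the one-sided error at the margin would be about 5.5% (1.96/√1.5 = 1.60, upper tail 0.055). That is a separate issue, and the covariate does not resolve it.

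**Conclusion.** The point holds as an optional improvement in precision, with medium confidence. The two models leave out a pre-randomisation rating that appears to be collected, and this omission in itself causes neither bias nor type I error inflation.

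For r of 0.3 to 0.5 the comfort distance to the limit shortens by 0.10 to 0.29 point with independent eyes (2.13 − 2.03; 2.13 − 1.84), or by 0.13 to 0.40 point with fully correlated eyes handled correctly (3.01 − 2.88; 3.01 − 2.61). Power at a true difference of 0 gains under 0.5 percentage point in the first case and 2.5 to 6.2 points in the second.

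These sizes rest on the assumed r, on the Study #872 SDs not being baseline-adjusted, and on the screening form carrying scales 3 and 12. The documents do not establish that a baseline for each eye exists, and nothing in the planned conclusion depends on making the change.

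**What to change.** First check the Initial Lens Performance form for scales 3 and 12, and whether they are recorded by eye. If the scales are there:

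- Add one linear covariate to each model: the Screening habitual-lens rating of the same scale (Overall Comfort for comfort, Vision for vision). Use the same eye's rating, or the subject's single rating for both eyes if the form is not by eye. Keep treatment, site and lens group.
- Replace a missing baseline by the pooled mean over both arms.
- Use the same model and rule in the per-protocol, best/worst-case, tipping-point and lens-group re-runs. The lens-group factor drops out of the last.
- Show the planned ANOVA as supplementary.

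Make the change by SAP amendment before database lock, the cut-off in SAP section 1, and before the analysis team is unmasked, in line with Protocol 8.0. A Clinical Monitor is unmasked before lock by design (Protocol 4.6), so the amendment should state whose masking counts. The documents do not show whether either point has passed. If either has, keep the planned ANOVA as primary and report the adjusted model only as supplementary in the clinical study report.

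The cost is slightly more programming, a documented change to two of the four co-primary models, and a note for the affected tables, since the table-format companion was not updated for SAP V2. No new data are needed if the form is confirmed. The margin and the difference-in-means estimand stay the same.
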